### **11.2 Other baseline characteristics**

For parameters collected on more than 1 occasion during the trial including baseline, the assessment at baseline will be presented with assessments collected later on in the trial and not in a separate table. These parameters are:

- Efficacy outcome parameters, e.g., pain intensities (current, average, and worst), questionnaires, and CRPS severity score (including signs and symptoms of CRPS).
- Laboratory parameters.
- Twelve-lead electrocardiogram (ECG) parameters.
- Vital signs parameters.
- Bone turnover markers.
- Health economics questionnaires (WPAI-CRPS, medical resource utilization).

Moreover, the analysis of the urine drugs of abuse test at the Enrollment Visit is described in Section [15.2.1](#).

### **11.3 Subject medical history**

#### **11.3.1 Medical history**

All medical history data will be presented in a subject data listing.

Medical history will be summarized and sorted alphabetically, separately for prior and concomitant diseases, by primary System Organ Class (SOC) and Preferred Term (PT). The number of subjects will be displayed for each SOC and PT.

### **11.3.2 Dental history**

Dental history will be analyzed separately in the same way as the medical history.

### **11.3.3 Complex regional pain syndrome history**

All CRPS history data will be presented in a subject data listing.

The CRPS history will be descriptively summarized. Time since precipitating event, duration (time since onset of symptoms), and time since diagnosis will be calculated based on the date of Visit 1 and the corresponding CRPS-related dates reported in the eCRF, and will be summarized as continuous variables. Time will be displayed in years. The CRPS etiology (precipitating event), CRPS location, previous CRPS history, and imaging methods used to support prior diagnosis (or exclude other diagnoses) will be categorically summarized.

## **11.4 Prior and concomitant medication or therapy**

Therapies will only be displayed in the subject data listings.

Prior and concomitant medication is collected in the eCRF as per enrollment. For the analysis, the following algorithm will be used to define prior and concomitant medication:

- Prior is all medication stopped prior to the first dose of IMP, regardless of its start date.
- Concomitant is any medication not stopped before the first dose of IMP, regardless of its start date or medication started after the first dose of IMP.

Medication will be summarized and sorted alphabetically separately for prior and concomitant medication by Anatomical Therapeutic Chemical categories (Level 2: pharmacological or therapeutic subgroup and Level 3: chemical or therapeutic or pharmacological subgroup).

For each medication, the number of subjects will be displayed. In addition, the number of subjects with medication started after last dose of IMP will be displayed.

Medication or therapy started after last dose of IMP will be flagged in the subject data listing.

## **12 EXPOSURE AND COMPLIANCE**

Exposure and compliance will be analyzed overall, i.e., for the single treatment group neridronic acid 400 mg, for the SAF.

All exposure and compliance data will be presented in subject data listings.

### **12.1 Exposure**

At each infusion visit (Visits 2, 3, 4, and 5), the full contents of an 8 mL ampule or vial will be transferred to an infusion bag containing 500 mL normal saline and administered by slow intravenous infusion.

The volume of IMP transferred to the infusion bag, the administered volume of the infusion, and the dose (amount of neridronic acid) and the cumulative dose will be listed by visit. For dose and cumulative dose, the actual and the planned dose will be displayed.

Actual dose and actual cumulative dose will be descriptively summarized by visit.

## 12.2 Compliance

At each infusion visit (Visits 2, 3, 4, and 5), compliance (%) will be calculated as the ratio of the dose actually administered, divided by the planned dose (100 mg). Moreover, the cumulative compliance will be derived at each infusion visit as the ratio of the actual cumulative dose divided by the planned cumulative dose. Compliance and cumulative compliance will be descriptively summarized by visit.

Cumulative compliance at Visit 5 will be classified based on the following 4 intervals 0 - 25%, >25 - 50%, >50 - 75%, and >75% - 100%, and a descriptive summary will be presented.

In addition, a categorical summary of infusion data in the eCRF (questions “*Was the IMP administered to the subject?*”, and “*Was dose completely administered?*”) will be created by visit.

## 13 EFFICACY ANALYSES

All efficacy data will be analyzed overall, i.e., for the single treatment group neridronic acid 400 mg, for the FAS, unless specified otherwise.

All efficacy data will be presented in subject data listings.

Missing efficacy data will not be imputed in this trial. The number of missing values will be included in all descriptive summaries.

### 13.1 Primary endpoint

Not applicable. No primary efficacy endpoint is defined for this trial.

### 13.2 Secondary endpoints

All secondary efficacy endpoints will be analyzed for the FAS and additionally for the TCS.

The following secondary efficacy endpoints will be analyzed overall and by subgroups:

- Change from baseline to Week 12 and Week 26 in the current pain intensity score, using a numerical rating scale (NRS).
- Response to treatment, defined as at least 30%, at least 50% and at least 2 points on the NRS decrease from baseline in the current pain intensity score, at Week 12 and Week 26.
- Patient Global Impression of Change (PGIC) at Week 12 and Week 26.
- Change from baseline to Week 12 and Week 26 in the Pain Interference score of the Brief Pain Inventory (BPI).

Since this is a single-arm trial, no hypothesis testing of secondary efficacy endpoints between treatment arms is planned. All secondary efficacy endpoints will be analyzed descriptively.

### 13.2.1 Main analysis

This section defines the main analysis for the secondary efficacy endpoints.

#### 13.2.1.1 Current pain intensity

Current pain intensities and the corresponding changes from baseline will be presented in a subject data listing. Baseline current pain intensities will be flagged in the listing. Current pain intensities including their changes from baseline will be descriptively summarized by visit.

The change from baseline values at all post-baseline visits from Visit 3 through Visit 11 will be analyzed using a mixed model for repeated measures (MMRM), including the covariate baseline pain intensity, and the factors pooled site and visit as fixed effects, and subject as random effect. An unstructured covariance matrix will be used to model the covariance structure. The degrees of freedom of the denominator will be estimated using the Kenward-Roger approximation ([Kenward and Roger 1997](#)).

If the default Newton-Raphson algorithm used by statistical analysis software (SAS) PROC MIXED fails to converge, the Fisher scoring algorithm up to iteration 2 will be used (via the SCORING=2 option of the PROC MIXED statement) to obtain the initial values of covariance parameters ([Mallinckrodt et al. 2008](#)). If this alternative also fails to converge, then in addition the no-diagonal factor analytic structure (via the TYPE=FA0(T) option of the REPEATED statement, where T=9 is the total number of post-baseline visits, visits 3 to 11) will be used, which effectively performs the Cholesky decomposition of the covariance matrix and is numerically more stable. The first algorithm that leads to convergence in this sequence of fallback measures will be the algorithm used for the primary analysis of the trial.

Point estimates (LSmeans), standard errors, and 95% CIs for the factor visit in the MMRM model representing the change from baseline at each visit will be presented. A graphical plot of the model-based estimates and the 95% CI of the change from baseline of current pain intensity scores will be created.

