**Handling of missing data**

Missing data will not be imputed in this trial. The number of missing data will be included in all descriptive summaries.

A mixed-effects model for repeated measurements (MMRM) will be conducted on the observed values of the change in current pain intensity score. An MMRM leads to unbiased estimates if the missingness mechanism is missing-at-random. Due to the long-acting effect of neridronic acid, missing-at-random is considered a clinically plausible assumption. The MMRM in this trial will include pooled site, baseline pain intensity and week as fixed effects and subject as a random effect. An unstructured covariance matrix will be used to model the covariance structure. Least squares means, standard errors, and 95% confidence intervals for the change from baseline will be obtained.

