**Handling of missing data**

Missing data will not be imputed in this trial. The number of missing data will be included in all descriptive summaries.

An MMRM will be conducted on the observed values of the change in current pain intensity score. An MMRM leads to unbiased estimates if the missingness mechanism is missing-at-random. Due to the long-acting effect of neridronic acid, missing-at-random is considered a clinically plausible assumption. The MMRM in this trial will include the covariate baseline pain intensity and the factors pooled site and visit as fixed effects, and subject as random effect. An unstructured covariance matrix will be used to model the covariance structure. Least squares means, standard errors, and 95% confidence intervals for the change from baseline will be obtained.

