## 8.2 Definitions

### 8.2.1 Definition of subgroups

Two subgroups will be defined based on the duration of CRPS:

1. Subjects with duration  $\leq 2$  year from onset of symptoms suggestive of CRPS.
2. Subjects with duration  $>$  year from onset of symptoms suggestive of CRPS.

When subgroup analyses are specified, the analysis will be performed separately in each of the subgroups and overall.

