### **13.3.1 Average and worst pain intensity**

Worst and average pain intensities will be added to the subject data listing of current pain values (see Section 13.2.1.1). The listing will be presented by pain type (average, current, and worst).

Worst and average pain intensities will be added to the descriptive summary of current pain. The summary will be presented by pain type.

Change in the worst pain intensity and average pain intensity for all post-baseline visits will be analyzed using the same statistical model as the one used for the current pain.

Point estimates least square means (LSmeans), standard errors, and 95% CIs for the factor visit in the MMRM model representing the change from baseline at each visit will be presented. Results will be added to the model-based summary of current pain.

Graphical plots of the model-based estimates and the 95% CI of the change from baseline of worst and average pain intensity will be created. The plots will be added to the graphical plots of current pain intensity scores.

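### Does pairing a random subject effect with a 9x9 unstructured covariance matrix undermine the pain MMRM?

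*SAP*

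**What the plan says.** SAP 13.2.1.1 models change from baseline in current pain at Visits 3 to 11, with baseline pain as covariate, "and the factors pooled site and visit as fixed effects, and subject as random effect. An unstructured covariance matrix will be used". Denominator degrees of freedom are Kenward-Roger. The protocol has the same pairing. In 1.5.3 the terms are "pooled site, baseline pain intensity and week as fixed effects and subject as a random effect", in 14.1.7 they are "the factors pooled site and visit as fixed effects, and subject as random effect", and an unstructured matrix follows each time.

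If the fit does not converge, the SAP first takes starting values from Fisher scoring (SCORING=2). It then adds the Cholesky-type structure, "via the TYPE=FA0(T) option of the REPEATED statement, where T=9 is the total number of post-baseline visits". The first algorithm that converges "will be the algorithm used for the primary analysis of the trial", although SAP 13.1 states: "No primary efficacy endpoint is defined for this trial".

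Under SAP 13.3.1, worst and average pain "will be analyzed using the same statistical model as the one used for the current pain". Secondary efficacy endpoints are analysed in the Full Analysis Set and the Treatment Completers Set, overall and by CRPS duration; under SAP 8.2.1 "the analysis will be performed separately in each of the subgroups and overall". The LS means are reported by visit, with no weights stated for the five pooled sites of SAP 8.2.2.

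**The concern.** A random subject intercept adds one constant to every element of the within-subject covariance matrix. An unstructured matrix can already absorb that constant, so the intercept variance cannot be estimated separately. The likelihood is flat in one direction and the information matrix for the covariance parameters is singular. The possible symptoms are non-convergence, a Hessian that is not positive definite, or a Kenward-Roger step that depends on how the software inverts a singular matrix. Neither fallback step removes the cause.

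Up to 8 fits are exposed: current pain in 2 analysis sets x 3 groups (overall and two duration subgroups) = 6, plus worst and average pain in the Full Analysis Set. The subgroup fits have fewer subjects. A contract research organization programs from this text (SAP 3), and the full SAS output goes into the trial report (SAP 20.2).

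Two lesser points sit beside it. The paragraph speaks of a primary analysis in a trial with no primary efficacy endpoint. And unstated LS-mean weights feed straight into the reported mean, because there is no comparator arm to cancel them.

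**Working it through.** **Inputs.** Post-baseline visits T = 9, five pooled sites (four US regions and the EU) and about 290 subjects, from SAP 13.2.1.1, 8.2.2 and 5.2. Variances, dropout and pool sizes are not in the documents, so those used below are assumptions.

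**The plan's own figure.** Visits 3 to 11 inclusive: 11 - 3 + 1 = 9, which agrees with the SAP.

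**Parameter count.**
- Unstructured: T(T+1)/2 = 9 x 10/2 = 45.
- FA0(q) with q = T = 9: q(2T - q + 1)/2 = 9 x 10/2 = 45.
- Either one plus a subject variance: 45 + 1 = 46, for 45 distinct elements of the marginal covariance matrix V.
- Rank of the derivative matrix of those 45 elements: 45 of 46 columns for unstructured plus intercept, and 45 of 46 for FA0(9) plus intercept. Without the intercept FA0(9) has full rank, 45.

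So the redundancy is real under the literal reading, and it survives both fallback steps.

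**Does it change the model?** Write V = R + sJ, where J is the all-ones matrix and s the subject variance. Take any positive-definite V. Every s from 0 up to, but not including, 1/(1'V^-1 1) leaves R = V - sJ positive definite and returns the same V. With s = 0 every V can be reached. The two specifications therefore describe the same set of distributions, and LS means and model-based standard errors depend on V alone.

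**Numerical checks (assumed data, not run in PROC MIXED).**
- Arbitrary V, 290 subjects: the log-likelihood was -4752.842599 at s = 0, 30%, 60% and 90% of its admissible maximum.
- 290 subjects, SD 2.5, 20% dropout, 14 fixed-effect parameters: with s at 0, 0.88, 1.75 and 3.15 the REML log-likelihood stayed at -4848.265329, the Visit 8 mean at -1.712 and its standard error at 0.164. The condition number of the covariance-parameter information matrix was 789 with 45 parameters and 6.2e16 with 46.
- Satterthwaite degrees of freedom for Visit 8 in that fit: 288.5 with 45 parameters, 288.5 with 46 and a generalized inverse, and 259 with 46 and an ordinary inverse, which is rounding noise. The 95% half-widths are 1.968 x 0.164 = 0.3228 and 1.969 x 0.164 = 0.3229.
- A separate fit by Fisher scoring with a generalized inverse (290 subjects, about 20% dropout): the 45- and 46-parameter models each converged in 6 iterations, with REML value -1939.964704, Visit 8 mean -1.748957 and standard error 0.152409 in both.

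**LS-mean weights.** Equal weights over five pools differ from subject-share weights by at most (range of regional means) x sum of max(0, 0.2 - n_r/290). Per 1 NRS point of regional range, with assumed pool sizes:
- 58 in each pool: 0.
- 66/62/58/54/50: 0.014 + 0.028 = 0.04.
- 80/70/60/50/30: 0.028 + 0.097 = 0.12.
- 90/80/60/40/20: 0.062 + 0.131 = 0.19.

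These are upper bounds. The documents give neither pool counts nor any regional difference.

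**The case for a change.** The case for editing the text is that the pairing appears in three places, so it is not a one-off slip. Nothing says that the random effect means only the clustering unit, and SAP 20.1.4 adds no efficacy definitions. A programmer who follows the words exactly would write both a RANDOM and a REPEATED statement. If the fit then failed, each listed fallback would carry the same redundancy, and a remedy would have to be found after database lock.

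The count and the point about the fallbacks stand. The consequence does not. Dropping the redundant term leaves the model unchanged, so doing it after lock gives no room to choose between results. No failed fit has been shown, and a 46-parameter fit reached the same values as the 45-parameter one. Two limits remain: PROC MIXED itself was not run, and the Kenward-Roger-adjusted standard error was not computed.

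On weighting, it is fair that a single-arm mean carries its weights with it. But equal weights, the PROC MIXED default, are a legitimate and determinate convention, and SAP 8.2.2 aims for pools of similar size. Weighting by each pool's share of treated subjects would be debatable too, and would not fit the completers or duration-subgroup analyses as it stands. A baseline-by-visit interaction would be a modelling preference; its absence is not an error.

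**Conclusion.** No change is needed. The phrase about subject is loose wording for within-subject correlation. The model is named an MMRM, its covariance structure is placed on the REPEATED statement, and the SAP mentions no RANDOM statement, so an analyst would put subject there as the clustering unit. Under the literal reading there is one redundant parameter (46 at rank 45). It changes neither the LS means nor the model-based standard errors, and the largest artefact seen was 1.969 against 1.968 in the 95% multiplier. The parameter count and the equivalence of the two models need only T = 9; the numerical illustrations rest on assumed variances and dropout.

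The stakes are also low. Protocol 1.5 and 14.1.2 plan exploratory analyses with no inferential testing, SAP 13.2 treats secondary efficacy as descriptive, and observed changes are summarised at each visit beside the model. The primary endpoint, occurrence of any TEAE, is untouched. The reference to a primary analysis is clerical, since SAP 13.1 rules out a primary efficacy endpoint. The LS-mean weights follow a determinate default, and the 0 to 0.19 range for a different choice rests on assumed pool sizes and a 1-point regional range.

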#### 13.2.1.2 Response to treatment

For each subject, the percentage change from baseline in current pain intensity will be calculated at each post-baseline visit (Visit 3 through Visit 11):

$$\%Change = \frac{Pain\ Intensity - Baseline}{Baseline} \cdot 100\%.$$

If the decrease is at least 30%, at least 50%, or at least 2 points on the NRS, the subject will be considered a responder for the respective threshold. If a subject shows a worsening or the pain intensity score is missing, the subject will not be considered a responder. This applies also to subjects with premature discontinuation where subsequent pain values are missing.

The percentage change from baseline, and the responder status (responder *Yes/No*) with respect to the 3 responder definitions will be presented in a subject data listing.

Descriptive summaries of the responder status will be presented by visit for each of the 3 responder definition. This includes the summary of the secondary responder endpoints, i.e., the response to treatment defined as at least 30%, at least 50% and at least 2 points on the NRS decrease from baseline at Week 12 (Visit 8) and Week 26 (Visit 9).

A graphical plot of the responder rates will be created by responder definition and visit.

For each of the 3 responder definitions, persistence of the treatment effect will be assessed by deriving a combined responder status for the following 3 time periods:

- Months 3 and 6 (Visit 8, and 9).
- Months 3, 6, and 9 (Visit 8, 9, and 10).
- Months 3, 6, 9, and 12 (Visit 8, 9, 10, and 11).

A subject is a combined responder if he/she is a responder at each of the visits mentioned in the definition of the respective time period. For the derivation of the combined responder status, the results of the individual visits are combined.

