### **1.4.3 Prior/concomitant medications or therapies**

Enrolled subjects must have failed trials of at least 2 treatments for CRPS, 1 of which must be a pharmacologic treatment. A failed trial is defined by continuing pain. Such treatments may be prior to or continuing at enrollment and can include any analgesic medication (including non-steroidal anti-inflammatory drugs [NSAIDs], opioids, antidepressants, etc.), interventional therapy (e.g., nerve block or spinal cord stimulation), or physical therapy.

Subjects are encouraged to continue standard of care interdisciplinary treatment for CRPS, including follow-up for physical therapy, occupational therapy, cognitive behavioral therapy, and graded motor imagery (including mirror feedback).

Subjects may continue treatment with allowed concomitant medications and therapies, including opioids and other analgesics, if they are on a stable, well-defined treatment regimen for at least 1 month prior to treatment and are anticipated to be able to maintain the treatment regimen, in the opinion of the investigator. Stable therapies, such as spinal cord stimulation, may be continued during the trial if they are stable for at least 1 month prior to the start of treatment. Changes to concomitant medications and therapies (e.g., use of short acting opioids for CRPS flares) may be allowed during the course of the trial and must be discussed with the medical monitor and documented in the case report form (CRF).

Sites will provide subjects with supplemental calcium and vitamin D, starting from Visit 1 and continuing through to the end of the trial. Acetaminophen (paracetamol) is recommended for

prophylaxis and treatment of flu-like symptoms that are commonly associated with the first intravenous administration of bisphosphonates (see Section 8.2 for details).

The following are forbidden as concomitant medications and therapies during the trial:

- Drugs with the potential to cause hypocalcemia (e.g., aminoglycosides). Subjects on a stable dose of furosemide or other loop diuretics may receive treatment with IMP as long as no dosage changes in the diuretic medications are anticipated and calcium levels are in the reference ranges.
- Oral or intravenous bisphosphonates, calcitonin, denosumab, or other bone-active drugs (e.g., teriparatide).

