## 1.5 Statistical analyses

As this is a single-arm trial, no treatment comparisons will be conducted, but development from baseline over time will be investigated. All analyses in this trial will be of exploratory nature. No statistical testing of inference is planned in this trial. There will be no multiplicity adjustment for any of the analyses. All confidence intervals used to describe the data will be determined using a 95% confidence level.

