### 1.5.1 Sample size rationale

The sample size is intended to maximize available safety data in line with the FDA regulatory requirements to support product registration. It is estimated that approximately 290 subjects will be included in this trial.

If the expected number of bone biopsies or bone densitometry and MRI assessments are not obtained, it is not planned to increase the number of subjects included in the trial.

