## 8.2 Benefit/risk analysis

Potential benefits to subjects participating in this trial may include a reduction in pain and other symptoms of CRPS, as well as benefits of medical supervision from being in a clinical trial.

Risks to subjects participating in this trial are primarily related to the known side effects of neridronic acid and bisphosphonates as a class, particularly those associated with intravenous administration. Although doses of up to 400 mg of neridronic acid have been administered safely in subjects with Paget's disease or CRPS-I, most of the clinical experience for neridronic acid has been at doses of 200 mg or below. In addition to drug-specific risks, there are also the risks of the procedures used in the trial.

In order to minimize the risk for the subject, it is obligatory that the investigator becomes familiar with all sections of the current neridronic acid investigator's brochure prior to the initiation of the trial and follows the warnings and directions thereof.

The trial population described in this protocol will consist of subjects with a diagnosis of CRPS and who are medically stable and in stable follow-up therapy for CRPS for at least 1 month.

Subjects will continue to receive stable therapy for CRPS. Additional pain medication may be prescribed in the event of severe pain flare, with notification of the sponsor. Changes in analgesic medications and other treatments for CRPS may be permitted during the follow-up period. This will help to ensure that subjects in the trial will not suffer from untreated pain. Subjects may withdraw from the trial at any time, without giving a reason and without prejudice. However, subjects who withdraw will be asked to continue follow-up visits if at all possible for the scientific integrity of the trial as well as for their own safety.

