### 12.2.2 Prior and concomitant medication or therapies

All medication requiring prescriptions (including oral contraceptives), over-the-counter medication, and therapies used within 3 months prior to enrollment and up to the end of the trial must be recorded in the CRF. Any change in dosage, regimen, or route, must be recorded in the CRF as a new entry.

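### Pain responder rates and MMRM means can overstate the effect of neridronic acid, because CRPS treatment changes allowed during follow-up are never linked to the pain results

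*SAP*

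**What the plan says.** **Treatment changes are permitted and recorded.** Protocol 1.4.3 states: "Changes to concomitant medications and therapies (e.g., use of short acting opioids for CRPS flares) may be allowed during the course of the trial". They must be discussed with the medical monitor and documented. Protocol 8.2 adds: "Changes in analgesic medications and other treatments for CRPS may be permitted during the follow-up period". It also allows extra pain medication for a severe flare. On data capture, Protocol 12.2.2 requires: "Any change in dosage, regimen, or route, must be recorded in the CRF as a new entry".

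**The pain analyses do not use this information.** SAP 13.2.1.2 defines response by a fall in current pain of at least 30%, at least 50% or at least 2 NRS points at the visit. A subject short of the threshold is a non-responder, and the SAP adds: "If a subject shows a worsening or the pain intensity score is missing, the subject will not be considered a responder". The combined status over Months 3 to 6, 9 or 12 is built from these visit results and is presented as showing how long the effect of treatment lasts. The MMRM in SAP 13.2.1.1 contains baseline pain, pooled site, visit and subject. Protocol 1.5.3 says that it uses observed values.

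**What is reported elsewhere.** SAP 11.4 counts, by ATC class, the subjects with medication started after the last infusion. For non-drug treatment it says: "Therapies will only be displayed in the subject data listings". SAP 10.3 has a deviation category, PD04, for inappropriate concomitant medication. SAP 13.2.2 (sensitivity analysis) and 13.2.3 (other analysis) are marked as not applicable, and SAP 20.1.4 has no trial-specific efficacy rules. The second efficacy set, the Treatment Completers Set, is defined by infusions received.

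**The concern.** The permitted changes are meant to relieve the pain that the endpoint measures. A subject who adds an analgesic and then scores below the threshold is counted under the heading of response to treatment, and the same score enters the MMRM mean. With a control arm, such relief would occur in both groups and partly cancel. Here it cannot.

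Forbidden procedures are not handled differently. Table 1 in Protocol 9.3.1 does not name them as a reason to leave the trial, and discontinuation of IMP applies only to the treatment period. A pain score obtained after such a procedure is analysed like any other.

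Efficacy is a stated secondary objective, and Protocol 6.4 places the trial in a registration package. A reader of the Week 12 and Week 26 rates would want to know how much of the reported response coincides with other treatment. No planned output shows it.

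**Working it through.** The documents contain no figure to reproduce here. Protocol 1.5.1 says "It is estimated that approximately 290 subjects will be included in this trial", with no formula behind it. No document gives the share of subjects who change treatment, so everything below is a range under assumptions.

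**Inputs from the documents**
- N = 290 (Protocol 1.5.1), with a 95% confidence level (Protocol 1.5).
- R, the reported responder rate: 32.5% and 73.2% are borrowed as bounds from the earlier placebo-controlled trial (Protocol 6.3: at least 50% decrease at 40 days, placebo and neridronic acid). 50% is added as a midpoint.

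**Assumed inputs**
- q, the share of responders with new or increased CRPS treatment: 5% to 30%.
- p, the share of all subjects with such treatment: 10% to 30%.
- x, the NRS points due to that treatment: 0.5 to 2.
- SD of the pain change: 2 to 3.

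**1. Responder rate if those responders count as non-responders: R(1 − q)**

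| R | q = 5% | q = 20% | q = 30% | 95% half-width, 1.96√(R(1−R)/290) |
|---|---|---|---|---|
| 32.5% | 30.9% | 26.0% | 22.8% | 5.4 points |
| 50.0% | 47.5% | 40.0% | 35.0% | 5.8 points |
| 73.2% | 69.5% | 58.6% | 51.2% | 5.1 points |

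The drop is R × q. It runs from 0.325 × 0.05 = 1.6 points to 0.732 × 0.30 = 22.0 points. It passes the half-width once q exceeds 5.4/32.5 = 17%, 5.8/50 = 12% or 5.1/73.2 = 7%.

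This drop is not the bias, because some of these subjects would have responded without the added treatment. The bias is the share of subjects who intensify treatment times the share who cross the threshold because of it. Assuming 5% to 20% and 30% to 50%, it is 0.05 × 0.3 = 1.5 points (4 of 290) to 0.20 × 0.5 = 10 points (29 of 290). The second factor is a counterfactual that this trial cannot observe.

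**2. Mean change in pain: shift = p × x**

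From 0.10 × 0.5 = 0.05 to 0.30 × 2 = 0.6 NRS points. The 95% half-width of a raw mean, 1.96 × SD/√290, is 0.23 (SD 2) to 0.35 (SD 3).

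**3. How little relief is needed**

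Entry requires current pain of at least 4. For a subject at 4, a fall of 2 points is 2/4 = 50% and meets all three definitions.

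**4. A force in the other direction**

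Missing scores count as non-response. If a share m is missing and the rate among those observed is 50%, the reported rate is 50% × (1 − m). At an assumed m = 20% this is 40.0%, the same 10-point drop as q = 20% gives in step 1. It does not touch the MMRM, which uses observed values.

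**The case against.** The strongest reply is that this is a safety trial whose primary endpoint is the occurrence of any TEAE, and that the protocol promises nothing confirmatory: "No statistical testing of inference is planned in this trial". Protocol 8.1 already asks for caution because there is no comparator. Using scores whatever other treatment is taken is a legitimate treatment-policy summary. Placebo response and regression to the mean would remain after any repair. All of this stands, and it limits the priority of the point. It does not remove it: the SAP never declares that strategy, and a general caution does not tell the reader how many responders changed treatment.

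A reader might infer three stronger things that the documents do not support.

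- *That the SAP ignores treatment changes altogether.* It does not. SAP 11.4 tabulates medication started after the last infusion, and PD04 captures inappropriate use. What is missing is the link to pain outcome. The ATC count is not by visit and, because every dose change is a new entry, it may not separate increases from reductions.
- *That late treatment creates persistent responders.* A combined responder must respond at every listed visit, starting at Week 12. Treatment added after Week 12 can only help to keep an existing responder above the threshold.
- *That anyone who adds treatment should be a non-responder from then on.* One short-acting dose for a flare would then fix non-response through Week 52, although the endpoint is pain at the moment of the visit. The lower rate would follow by construction.

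There is also a fair objection to censoring MMRM scores after a treatment change. Protocol 1.5.3 supports missing-at-random by the drug's long-acting effect, not by removal of scores triggered by a flare. Follow-up visits are 4 to 14 weeks apart, so the flare itself may never be observed. Dropping later scores could even flatter the mean.

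**Conclusion.** The gap is real: neither the responder rule, the MMRM nor any planned table relates new or increased CRPS treatment to the pain result. The rates and means can therefore overstate the effect of neridronic acid.

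A reader might conclude that they do overstate it. The documents do not show that. Upward is the probable direction, since added treatment is given to relieve pain. However, reductions in other treatment would hide benefit, and scoring missing as non-response lowers the responder rates. The size is unknown. The ranges of 1.6 to 22.0 points for reclassification, 1.5 to 10 points for bias and 0.05 to 0.6 NRS points for the mean rest wholly on assumed shares and effects. They show only that modest shares could matter relative to the sampling error at 290 subjects.

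This is a worthwhile, inexpensive improvement in how secondary efficacy results are presented. It is not a flaw in the trial's primary purpose.

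**What to change.** 1. State in SAP 13.2.1 that the present responder rule and MMRM are treatment-policy summaries, using scores regardless of other CRPS treatment. Keep them as the main analyses.
2. Before database lock, have a medical review classify the CRF medication and therapy entries as (a) new or increased CRPS pain treatment, excluding acetaminophen given for the acute phase reaction, or (b) a therapy on the forbidden list in Protocol 1.4.3. Protocol 12.2.2 does not mention indication, so the review may need to judge this for some entries.
3. In SAP 13.2.1.2, show by visit (at least Weeks 12 and 26) and for each combined definition how many subjects, and how many responders, had such a treatment ongoing at the visit or within a pre-specified window before it.
4. Add a supplementary responder rate that counts those subjects as non-responders at the affected visits only, and derive the combined status from those visit results.
5. Optionally, in SAP 13.2.2, repeat the MMRM with affected scores set to missing. Label it a hypothetical-strategy analysis that relies on missing-at-random.

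The cost is SAP wording, one medical review of recorded entries and one extra table, plus one model run if item 5 is taken up. The supplementary rate cannot exceed the main one and, like it, does not isolate a drug effect without a control arm; the text should say so. No clinical rule changes.
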